1.0 Clinical Study Plan Overview

Objective:	To collect data on the performance of the Biodesign® Hernia Graft when used to reinforce soft tissues during ventral hernia repair.
Design:	Multicenter, open-label, prospective clinical study.
Primary performance endpoint:	Hernia recurrence through 1-year follow-up (hernia recurrence as defined in Appendix C).
Additional measures:	
The additional measures include summaries of the following:
 
• Device-, procedure-, and hernia-related adverse event rates through the 2-year follow-up period• Hernia recurrence rate through 2-year follow-up• Operative times• Duration of hospital stay• Hospitalization times for related Serious Adverse Events (SAEs)• Patient-reported quality of life
Number of patients:	95 patients
Number of clinical sites:	5 clinical sites initially, with the possibility to add up to 5 more sites (for up to 10 clinical sites in total) as needed to mitigate enrollment difficulties or other unforeseen challenges.
Patient participation duration:	Patients will be followed at a minimum of 30 days, 6 months, 1 year, and 2 years post-procedure.
Expected study duration:	It is expected that enrollment will begin within 1 month of the first site being eligible to enroll. Individual patient enrollment will last through procedure and 2-year follow-up. Total study duration (from study initiation through patient enrollment and follow-up) is expected to be 5-6 years.

2.0 Ethical Considerations and Regulatory Compliance

This clinical study will be conducted in accordance with the Clinical Study Plan, the ethical principles that have their origin in the Declaration of Helsinki, ISO 14155, and other applicable local regulations as appropriate.

3.0 Objectives of the Clinical Study

The primary objective of this study is to collect data on the performance of the Biodesign Hernia Graft when used to reinforce soft tissues during ventral hernia repair.

The primary performance endpoint is the rate of hernia recurrence as defined in Appendix C through 1-year follow-up.

Additional objectives of this clinical study are to:

- Summarize the adverse event rates for normal commercial use of the device (e.g., seroma and infection rates)
- Assess the long-term success of the device in the reinforcement of hernia repairs through 2-year follow-up

Additional measures to address these objectives include summaries of the following:

- Device-, procedure-, and hernia-related adverse event rates through the 2-year follow-up period
- Hernia recurrence rate through 2-year follow-up
- Operative times
- Duration of hospital stay
- Patient-reported quality of life

4.0 Device Description

4.1 Intended Use (Europe)

The Biodesign® Hernia Graft is intended for implantation to reinforce soft tissues where weakness exists during ventral hernia repair.

4.2 Intended Use (rest of world)

The Biodesign® Hernia Graft is intended for implantation for to reinforce soft tissues where weakness exists. Indications for use include the repair of a hernia or body wall defect.

4.3 General Device Description

The Biodesign Hernia Graft is a graft composed of porcine small intestine submucosa (SIS). The device is CE-marked (G7 039164 0116) and cleared by the United States Food and Drug Administration (FDA) (K133306) for clinical use. The device will be used according to the labeled indication and in accordance with the Manufacturer's Instructions for Use (IFU).

The device IFU contains the following information:

- Instructions for storage and handling requirements
- Precautions and preparation for use of the device
- Description of the procedures involved in the use of the device including recommendations for device placement

4.4 Device Identification and Tracking

The Biodesign Hernia Graft is commercially available and will be obtained by each institution through normal commercial channels. Tracking of individual devices within the study will not be performed; however, information such as the size of each device used in a patient will be documented and recorded on electronic case report forms (eCRFs).

5.0 Background Information

The Biodesign Hernia Graft is comprised of 8 layers of decellularized porcine small intestinal submucosa (SIS) that has been pressed-lyophilized (i.e., freeze-dried under vacuum pressure) to laminate the component sheets (i.e., layers) together. In addition, it is perforated and sewn with 4-0 Trisorb suture (polyglycolic acid (PGA); Samyang Corporation, Seoul, South Korea). The suture is distributed in a diamond pattern across the graft and along the periphery and is intended to mitigate delamination of the layers upon rehydration and/or manipulation during implantation. Being a completely biologic device, the Biodesign Hernia Graft is considered MR safe.

The Biodesign Hernia Graft is available in eight (8) sizes: 8 cm x 10 cm, 8 cm x 20 cm, 8 cm x 30 cm, 10 cm x 10 cm, 13 cm x 15 cm, 13 cm x 22 cm, 20 cm x 20 cm, and 20 cm x 30 cm. The graft is terminally sterilized using an established ethylene oxide (EtO) sterilization cycle that has been validated to a sterility assurance level of 10^{-6} . Sterilization is routinely monitored, calibrated, and operated in adherence with standardized procedures. The Biodesign Hernia Graft may be stored at room temperature

in a clean, dry location for up to 18 months.

The Biodesign Hernia Graft is a technology that has been used in the treatment of hernias and abdominal wall defects for nearly 10 years. This post-market clinical follow-up study is being performed to confirm the continued safety and performance of the Biodesign Hernia Graft when used in accordance with its approved labeling.

6.0 Risk Analysis and Risk Assessment

6.1 Risks and Possible Adverse Reactions

Foreseeable adverse events associated with the use of the Biodesign Hernia Graft and other biologic graft prostheses are described in the IFU and will be collected in this study and reported as an additional measure.

Please reference the IFU for the following:

- Contraindications
- Warnings
- Precautions

The use of this FDA cleared device does not introduce any new or additional risk to standard ventral hernia procedures using biologic mesh materials.

Because the Biodesign Hernia Graft is cleared for general use in this patient population, the only additional patient risk associated with participation in this study is accidental release of protected health information.

6.2 Methods to Minimize Risks

In order to minimize the risks noted in the IFU, the procedure for proper use of the Biodesign Hernia Graft described in the IFU will be followed. In addition, only qualified surgeons with surgical training and experience in ventral hernia repairs will be involved in the study. Finally, the capture, handling, and storage of the study data are done in compliance with applicable regulations to minimize the risk of release of any personal health information.

6.3 Anticipated Clinical Benefits

There is no direct benefit for the patient regarding participation in this study, other than the benefit of having scheduled follow-up visits for two years to follow their general health status and outcome. However, it is important to gain more knowledge of the

performance of the Biodesign Hernia Graft in normal clinical use. The increased knowledge of the use of the product in this patient population will be beneficial for future patients and society as a whole.

7.0 Design of the Clinical Study

7.1 Design of the Clinical Study

This multicenter, open-label, prospective clinical study will evaluate the performance of the Biodesign Hernia Graft to reinforce soft tissues during ventral hernia repair.

This post-market study will enroll up to 95 patients at up to 10 clinical sites. Each clinical site will be limited to a maximum of 50 patients to ensure a variety of patients and surgical techniques are represented. There is no minimum enrollment number per site.

7.2 Study Design Rationale

This study has been designed as a multicenter, open-label, prospective study to collect data on the performance of the Biodesign Hernia Graft. The inclusion and exclusion criteria for this study have been selected based on the instructions outlined in the IFU so that the results from this study can provide data on the real world use of the device.

7.3 Duration of the Study and Patient Participation

Patient enrollment is expected to be completed within 3-4 years of study initiation. Total study duration (from study initiation through patient enrollment and follow-up) is expected to be 5-6 years.

Patients are expected to participate in this study for 2 years (\pm 90 days) after the study procedure.

7.4 Measures to be Taken to Avoid or Minimize Bias

This multi-center, open-label, prospective study is intended to collect information regarding the performance of the study device. Patients will be selected and included in accordance with the eligibility criteria and the need for a biologic graft to treat their hernia. In addition, the study will utilize uniform definitions for study endpoints. Study results will be analyzed in accordance with the prospectively defined analysis plan outlined in Section 11.

7.5 Endpoints

7.5.1 Primary Endpoint

The primary performance endpoint is the rate of hernia recurrence as defined in Appendix C through 1-year follow-up.

7.5.2 Additional Measures

Additional measures will include the following:

- Device-, procedure-, and hernia-related adverse event rates through the 2-year follow-up period
- Hernia recurrence rate through 2-year follow-up
- Operative times
- Duration of hospital stay
- Hospitalization times for related SAEs
- Patient-reported quality of life

7.5.3 Rationale for Endpoints

The endpoints and measures were chosen since hernia recurrence and adverse events related to the use of surgical grafts have been identified as issues of clinical interest; many of these events often result in additional surgical procedures. Furthermore, patient quality of life has been chosen as an additional measure to capture the outcome of the intervention from the patient's perspective. Using patient-reported outcomes measures, we will be able to evaluate abdominal wall function and patient's perception of pain independently of hernia recurrence.

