7.6 Variables to be Measured to Demonstrate Achievement of Endpoints

The endpoints and measures will be assessed as described in Table 7.6-1.

Table 7.6-1. Assessment of Endpoints and Measures

Endpoint / Measure	Assessment ¹
Hernia recurrence	Clinical examination
Rate of adverse events	Evaluation based upon reports of events submitted by the study sites
Rate of Surgical Site Occurrences (SSO)	Evaluation based upon reports of occurrences submitted by the study sites
Rate of Surgical Site Occurrences needing Intervention (SSOPI)	Evaluation based upon reports of occurrences submitted by the study sites

Patient quality of life	Postoperative assessment (patient questionnaire)
-------------------------	--

¹For the 1 and 2-year follow-up visits: Every attempt should be made to have the patient return for a physical exam at the 1-year and 2-year timepoints in order to determine hernia recurrence. Results from a physical exam made by a non-study physician (e.g. primary care physician) can be included if assessment at the clinical site is not possible.

If the patient refuses or is unable to return in person for the 1-year or 2-year physical exam, patient self-assessment of the presence of recurrence symptoms, patient responses regarding adverse events, and patient questionnaires may be obtained via telephone or email. If the patient self-assessment of the presence of recurrence symptoms suggests that a hernia is present, the patient should be contacted and requested to return for a physical exam for confirmation.

Patient reported outcomes will be tabulated and reported. The primary endpoint will be analysed as noted in Section 11.0.

Patient data will be documented by trained personnel at the clinical site and recorded onto eCRFs through an electronic data capturing (EDC) system. The assessment schedule is summarized in Table 7.6-2 and in Appendix B:

Table 7.6-2. Assessment schedule

	Pre-Procedure	Procedure	Follow-up			
			30 days (± 15 days)	6 month (± 30 days)	1 year (± 90 days)	2 years (± 90 days)
Consent	X					
Medical history	X					
Procedure Information		X				
Physical exam	X	X	X	X	X	X
Patient Reported Outcomes measures			X	X	X ^a	X ^a
Adverse events		X	X	X	X ^a	X ^a

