9.0 Methods

9.1 Pre-procedure Evaluation

Prior to patient enrollment, patients will undergo a baseline evaluation. Assessments will be completed as described in Table 9.1-1. All pre-procedure assessments are considered standard of care.

Table 9.1-1. Pre-procedure requirements

Pre-procedure	
Timing	Prior to the study procedure
Type	In-person
Assessment	Review study with patient and obtain written informed consent
	Clinical assessment including hernia assessment and symptomology
	Record patient demographics and pre-op evaluation

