9.4 Follow-up

Patients are expected to participate in this study for 2 years after the procedure. The follow-up visits will occur within the time frames listed below. Following the study procedure, assessments will be completed as described in Table 9.4-1.

Table 9.4-1. Follow-up requirements

30-day Follow-up (± 15 days)	
Timing	15-45 days following the study procedure
Type	In person
Assessments	Physical exam of the incision and abdominal wall
	Record specific data points within the EDC system
	Administer a postoperative assessment (patient questionnaire)
6- month Follow-up (± 30 days)	
Timing	153-213 days following the study procedure
Type	In person
Assessments	Physical exam of the incision and abdominal wall
	Record specific data points within the EDC system
	Administer postoperative assessment (patient questionnaire)
1-Year Follow-up (± 90 days)	
Timing	275 – 455 days following the study procedure
Type	In person ¹
Assessments	Physical exam of the incision and abdominal wall
	Record specific data points within the EDC system
	Administer postoperative assessment (patient questionnaire)
2-Year Follow-up (± 90 days)	
Timing	640 – 820 days following the study procedure
Type	In person ¹
Assessments	Physical exam of the incision and abdominal wall
	Record specific data points within the EDC system
	Administer postoperative assessment (patient questionnaire)

¹For the 1 and 2-year follow-up visits: Every attempt should be made to have the patient return for a physical exam at the 1-year and 2-year timepoints in order to determine hernia recurrence. Results from a physical exam made by a non-study physician (e.g. primary care physician) can be included if assessment at the clinical site is not possible.

If the patient refuses or is unable to return in person for the 1-year or 2-year physical exam, patient self-assessment of the presence of recurrence symptoms, patient responses regarding adverse events,

and patient questionnaires may be obtained from the patient via telephone or email. If the patient self-assessment of the presence of recurrence symptoms suggests that a hernia is present, the patient should be contacted and requested to return for a physical exam for confirmation.

Patient reported outcomes will be tabulated and reported. The primary endpoint will be analysed as noted in Section 11.0.

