APPENDIX B: Study Event Schedule

	Pre-Procedure	Procedure	Follow-up			
			30 days (± 15 days)	6 months (± 30 days)	12 months (± 90 days)	2 years (± 90 days)
Informed consent	X					
Medical history	X					
Procedure Information		X				
Physical exam	X	X	X	X	X ¹	X ¹
Patient Reported Outcomes measures			X	X	X ¹	X ¹
Adverse events		X	X	X	X ¹	X ¹

¹Every attempt should be made to have the patient return for a physical exam at the 1-year and 2-year timepoints in order to determine hernia recurrence. Results from a physical exam made by a non-study physician (e.g. primary care physician) can be included if assessment at the clinical site is not possible. If the patient refuses or is unable to return in person for the 1-year or 2-year physical exam, patient self-assessment of the presence of recurrence symptoms, patient responses regarding adverse events, and patient questionnaires may be obtained via telephone or email.

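### The quality-of-life questionnaire is given only after surgery, so the study can describe post-operative status but cannot estimate change from before the repair

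*Combined protocol and SAP*

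**What the plan says.** Quality of life is listed among the additional measures in Sections 1.0, 3.0 and 7.5.2. Section 7.5.3 gives the reason: "patient quality of life has been chosen as an additional measure to capture the outcome of the intervention" as the patient sees it. It goes on to say that with these measures "we will be able to evaluate abdominal wall function and patient's perception of pain independently of hernia recurrence".

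Table 7.6-1 describes the assessment as a post-operative patient questionnaire and names no instrument. In Table 7.6-2 and again in Appendix B, the row "Patient Reported Outcomes measures" is blank under Pre-Procedure and Procedure and marked at the four follow-up visits. Table 9.4-1 agrees, with the first questionnaire at the 30-day visit (15 to 45 days after the procedure).

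Table 9.1-1 sets out an in-person pre-procedure visit with consent, demographics and pre-operative evaluation, and "Clinical assessment including hernia assessment and symptomology". It lists no questionnaire, and Section 9.1 adds that "All pre-procedure assessments are considered standard of care".

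On analysis, Sections 7.6 and 9.4 say only that these outcomes will be tabulated. Section 11 contains no quality-of-life analysis, hypothesis or power statement. All enrolled patients receive the graft, and no comparison group is described.

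**The concern.** The outcome of an operation from the patient's side is usually read as how the patient fares afterwards relative to before. A study without a comparator can supply that contrast only from each patient's own pre-operative score, and this schedule does not collect one. A pain score at 1 year is then compatible with improvement, no change or worsening.

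The population makes this matter more. Eligibility covers primary and recurrent hernias (Section 8.0). Section 11.7 accepts acute and elective repairs, several techniques and any concomitant disease. Section 11.6 expects some sites to treat more advanced disease. Pre-operative pain and function are therefore likely to differ between patients, and differences in post-operative scores between sites or subgroups cannot be adjusted for them.

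Under Section 10.0, participation ends, and data collection with it, after a further procedure for recurrence or removal of the device. Later scores thus come from a selected group, and without a baseline the report cannot show whether those who remained had started out better. A missed pre-operative score cannot be recovered once the patient has been operated on.

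**Working it through.** **Step 1: the schedule.** The documents state no quality-of-life figure to reproduce, so the first check sets the relevant places side by side.

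| Place | Before surgery | After surgery |
|---|---|---|
| Table 7.6-1 | none | described as post-operative |
| Table 7.6-2 | blank | 30 days, 6 months, 1 year, 2 years |
| Table 9.1-1 | no questionnaire listed | not applicable |
| Table 9.4-1 | not applicable | same four visits |
| Appendix B | blank | same four visits |

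All five agree: 0 questionnaires before the procedure and 4 after it. Because separate tables show the same pattern, this is not a table damaged in conversion.

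**Step 2: whether anything else could serve as a baseline.** The symptom item in Table 9.1-1 is part of a clinical assessment and is not said to use the questionnaire. The 30-day score is taken during surgical recovery. A questionnaire with items comparing now with before surgery could give a recalled answer, but the documents do not say that this one has such items.

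**Step 3: what can be estimated.** Write Y0 for the pre-operative score and Yt for the score at visit t.
- The mean of Yt can be estimated at each of the four visits.
- The mean of Yt minus Ys, for two post-operative visits, can be estimated. A stable pre-operative level cancels from it within a patient, but contrasts that start at 30 days include recovery from surgery.
- The mean of Yt minus Y0, and any analysis of Yt adjusted for Y0, cannot be obtained, because Y0 is observed in 0 of 95 patients.

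**Step 4: what a baseline would offer, for scale.** The one input from the documents is n = 86, the evaluable number in Section 11.1, which was derived for recurrence. Assumptions: 86 complete pairs, equal SDs at both times, and a correlation r between 0.3 and 0.7. The documents give no SD or correlation.

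SE of mean change = SD × √(2(1 − r)) / √86, with √86 = 9.274.

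95% half-width = 1.96 × SE. Change detectable with 80% power at two-sided 0.05 = (1.96 + 0.84) × SE.

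| r | √(2(1 − r)) | SE (SD units) | 95% half-width | Detectable change |
|---|---|---|---|---|
| 0.3 | 1.183 | 0.128 | 0.25 | 0.36 |
| 0.5 | 1.000 | 0.108 | 0.21 | 0.30 |
| 0.7 | 0.775 | 0.084 | 0.16 | 0.23 |

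Fewer complete pairs would widen these in proportion to 1/√n.

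**The case against.** The strongest reply is that the plan is coherent on its own terms. It states no aim of improvement or of change from baseline. Quality of life is one of several additional measures to be summarised, and the assessment is openly labelled post-operative. Section 7.5.3 speaks of function and pain independently of recurrence, and post-operative scores set beside recurrence status can serve that use descriptively. This stands. A reader might infer that the study fails a promise to show improvement, or cannot address the patient's perspective at all, but the documents support neither reading. The gap is between a broad rationale and what post-operative scores alone can carry.

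A second reply is that a baseline would not secure attribution. Without a comparator, change before to after is still open to regression to the mean and to the concomitant procedures that Section 9.3 allows. This also stands: the gain is an estimate of change, not proof of cause.

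A third is that a reader might take all comparisons over time to be confounded by pre-existing pain. They are not, because a stable level cancels between post-operative visits. Nor would a baseline remove dropout bias. Missing later scores could also be modelled in part from earlier post-operative scores and recorded characteristics. A baseline adds information there but is not the only source.

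Finally, the change has practical limits: acute repairs, an unnamed instrument that may not suit pre-operative use, and enrolment that is counted only when the implant procedure is complete (Section 9.2). These affect how the fix is worded and do not remove the reason for it.

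**Conclusion.** The point holds in a limited form. As scheduled, the study can describe how patients feel at four times after repair. It cannot estimate change from before surgery for any patient, and it cannot adjust post-operative scores for pre-operative pain or function in a deliberately mixed population. That is narrower than the rationale in Section 7.5.3 suggests.

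The effect is confined to one additional descriptive measure. The primary recurrence endpoint, its sample size and its analysis are untouched. The schedule finding rests on agreement between all the tables and needs no assumption. The detectable changes of 0.23 to 0.36 SD are illustrative, since they rest on assumed correlations, equal SDs and 86 complete pairs. This is an inexpensive improvement worth making, not a defect that threatens the study's main conclusion.

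**What to change.** 1. In Table 7.6-2 and Appendix B, mark the patient-reported outcomes row in the Pre-Procedure column, and add a matching line to Table 9.1-1: the same questionnaire, after consent and before surgery, where feasible. Section 8.1 already places consent before study-specific assessments. Name the instrument and confirm that it can be completed before surgery.
2. Amend the Section 9.1 statement that every pre-procedure assessment is standard of care, since this one would be study-specific.
3. In Section 11.2, add a descriptive summary of change from baseline with a 95% confidence interval at each visit, with the number of complete pairs, beside the post-operative scores. A formal model is not needed for a measure that is only to be tabulated.
4. For patients without a baseline, limit conclusions to post-operative status. If no baseline is added, narrow the wording of Section 7.5.3 in the same way.

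The cost is one extra questionnaire at an existing in-person visit and a small amendment. Baselines may be missing in acute repairs, or may reflect the acute episode, and will be missing for anyone already implanted (the documents do not give enrolment status). Some will be collected from patients who never receive the graft and so never enter the study.
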